4.1 Study Population

The domain “Study Population” covers participant disposition, analysis sets, protocol deviations, demographics, baseline characteristics, medical history and concomitant disease, and prior and concomitant medications and procedures.

Study analysis populations are defined in Section [3.2](#).

The analysis set used for each analysis is specified in the relevant sections below.

4.1.1 Participant Disposition and Completion Status

4.1.1.1 Presentation

Participant disposition will be summarised, presenting the number of participants enrolled and the number and percentages of participants who did and did not receive treatment, who discontinued study intervention, who transitioned to capsule formulation, who entered the long-term safety follow-up (participants < 5 years of age after 25 cycles or discontinuation of study intervention), and who discontinued the study. A breakdown by reason for participants discontinuing study intervention and discontinuing from the study will be included in this summary. The number of participants ongoing on treatment and in the study at the time of the DCO will also be presented.

Summaries of data relating to the impact of the global/country COVID-19 situation will include the number who discontinued study intervention and withdrew from the study due to the global/country situation and listings for participants affected by the global/country situation.

Listings presenting details of discontinuations by individual participant will be produced for those enrolled participants discontinuing study intervention and discontinuing the study.

Disposition data will be presented for all enrolled participants.

4.1.2 Analysis Sets

4.1.2.1 Definitions and Derivations

The definitions and derivations of the analysis sets are described in Section [3.2](#).

4.1.2.2 Presentation

The number of participants in each analysis set and the reason for exclusion from each analysis set will be summarised.

A listing of individual participants not included in each analysis set will be provided.

4.1.3 Protocol Deviations

4.1.3.1 Definitions and Derivations

Protocol deviations will be defined as any change, divergence, or departure from the study design in the CSP. Prospective approval of protocol deviations to recruitment and enrolment criteria, also known as protocol waivers or exemptions, is not permitted.

Protocol deviations and IPDs are defined in the protocol deviation plan and will be finalised at the data review meeting before database lock. IPDs are identified from the complete set of protocol deviations. IPDs are those that may significantly impact the reliability of the study data or that may significantly affect a participant's rights, safety, or wellbeing.

4.1.3.2 Presentation

A summary table will be produced to show the number and percentage of participants with any IPD and by category of IPD.

The individual participant data for IPDs will also be listed.

IPD data will be presented for all participants in the safety analysis set.

4.1.4 Demographics

4.1.4.1 Definitions and Derivations

Date of birth (dd/mm/yyyy) and age are recorded on the CRF. Age at Screening will be calculated using date of birth and the Screening visit date, rounded to 1 decimal place. If Day of date of birth is missing or unknown (NA/mm/yyyy), Day = 1 (first day of the month) will be imputed for Age calculation (01/mm/yyyy).

Age at Screening = [(Screening visit date- date of birth)/365.25]

If Day and Month of birth are both missing or unknown, the Age recorded in the CRF will be used.

Age at Screening will used in the statistical analysis.

4.1.4.2 Presentation

A summary table of demographic data of age, sex, race, ethnicity, and country will be produced, and demographic data will be listed.

Demographic data will be presented for all participants in the safety analysis set.

4.1.5 Baseline Characteristics

4.1.5.1 Definitions and Derivations

Baseline BSA group will be defined as the BSA (m^2) range group used for the granule formulation dose schema for selumetinib:

- ≥ 0.40 to $< 0.50\ m^2$
- ≥ 0.50 to $< 0.60\ m^2$
- ≥ 0.60 to $< 0.70\ m^2$
- ≥ 0.70 to $< 0.90\ m^2$
- ≥ 0.90 to $< 1.10\ m^2$
- ≥ 1.10 to $\leq 1.29\ m^2$

4.1.5.2 Presentation

Characteristics of height, weight, and BSA (m^2) and BSA group at baseline will be summarised and listed.

Baseline characteristic data will be presented for all participants in the safety analysis set.

4.1.6 Disease Characteristics

4.1.6.1 Definitions and Derivations

Missing diagnostic dates will be imputed for the summary table as described in Section 3.3.6.2.

4.1.6.2 Presentation

A summary table of characteristics of time from diagnosis of NF1 to start of study intervention, time from diagnosis of inoperable PN to start of study intervention, reasons for inoperable PN (eg, PN encasement of vital structures, PN close proximity to vital structures, etc.), and NF1 diagnostic criteria (eg, any cafe-au-lait spots, bilateral freckles in axilla or groin, etc.) will be produced. Presence of non-target PNs, PN location, PN symptoms, PN laterality, PN measurability overall morbidity type and number of morbidities, incomplete coverage, and the reasons for incomplete coverage for both target and non-target PN will be included.

A listing of disease characteristics will be produced for individual participants. Results of any previous genetic testing for NF1 will be included in the listing only.

Disease characteristic data will be presented for all participants in the safety analysis set.

4.1.7 Medical History and Concomitant Disease

4.1.7.1 Definitions and Derivations

Medical and surgical history will be coded using the MedDRA [26.1 version or higher].

Prior PN therapy will be coded using the WHODrug Dictionary [2023.09 version or higher] ATC Classification codes.

Any medical history that is ongoing at the time of informed consent is considered current medical history; otherwise, it will be considered past medical history.

4.1.7.2 Presentation

The number and percentage of participants with prior PN therapy, prior radiotherapy, and surgical history will be summarised. A summary table of prior PN therapy will be produced by ATC code and generic term. A frequency table showing the number of participants with prior radiotherapy by ATC code and generic term will be presented. Summary tables of surgical history and past and current medical history will be produced by system organ class and preferred term.

The individual participant data for medical history (past and current), prior PN therapy, prior radiotherapy, and surgical history will also be listed.

Data will be presented for all participants in the safety analysis set.

4.1.8 Prior and Concomitant Medications and Procedures

4.1.8.1 Definitions and Derivations

Medications received prior to, concomitantly, or post-treatment are coded using the AstraZeneca Drug Dictionary ATC Classification codes.

For the purpose of inclusion in prior and/or concomitant medication or therapy summaries, incomplete medication start and stop dates are imputed as detailed in Section [3.3.6.1](#).

Prior, concomitant, and post-treatment medications and procedures are defined based on imputed start and stop dates as follows:

- Prior medications and procedures are those taken prior to study intervention with a stop date prior to the first dose of study intervention.

- Concomitant medications and procedures are those with a stop date on or after the first dose date of study intervention (and could have started prior to or during treatment).
- Post-treatment medications and procedures are those with a start date after the last dose date of study intervention.

Missing coding terms are listed and summarised as “Not coded”.

Procedures will be coded using the MedDRA (26.1 version or higher).

4.1.8.2 Presentation

The following summary tables of the number and percentage of participants by ATC code and ATC text will be produced:

- Summary of prior medications
- Summary of allowed concomitant medications
- Summary of disallowed concomitant medications
- Summary of post-treatment medications

All concomitant medications will be listed.

Medication data will be presented for all participants in the safety analysis set. Procedures will not be summarised but will be listed. The individual participant data for subsequent PN therapy will also be listed.

4.1.9 Study Intervention Compliance

This is covered in Section 4.6.1.

4.2 Endpoint Analyses

This section covers details related to the endpoint analyses such as primary, secondary, and other endpoints including sensitivity and supportive analyses.

The CCI [REDACTED] and CCI [REDACTED] analyses will not form part of the clinical study report and will not be handled by the statistical and programming vendor. The CCI [REDACTED] and CCI [REDACTED] analyses will be analysed and presented separately from the main clinical study report. Thus, they are outside the scope of this SAP.

Statistical category	Endpoint	Population	Population level summary (analysis)	Details in section
To determine the PK of selumetinib after administration of the selumetinib granule formulation				
Primary	Selumetinib AUC0-12 derived after single dose administration	PK	Descriptive statistics	4.4
To assess the safety and tolerability of the selumetinib granule formulation				
Primary	AEs, AESIs and SAEs. Duration of exposure and treatment compliance percentage. Absolute values and changes from baseline in Laboratory assessments. Vital signs, ECG, ECHO, ophthalmologic assessment, Knee (or wrist) MRI/X ray, and performance status.	Safety	Descriptive statistics	4.6
To assess the palatability of the selumetinib granule formulation				
Secondary	Palatability will be assessed using the parent-reported observer palatability assessment.	Safety	Descriptive statistics	4.2.3
To further assess the PK of selumetinib and N-desmethyl selumetinib metabolite after administration of the selumetinib granule formulation				

Statistical category	Endpoint	Population	Population level summary (analysis)	Details in section
Secondary	Single and multiple dose plasma concentrations and PK parameters of selumetinib and N-desmethyl selumetinib (see Section 4.4 for list of parameters).	PK	Descriptive statistics	4.4
To evaluate the efficacy of the selumetinib granule formulation by assessment of ORR as determined by ICR per REiNS criteria				
Secondary	ORR Safety ORR estimate and	4.2.5	two-sided 95% CI based on the exact CCI	

To evaluate the efficacy of the selumetinib granule formulation by assessment of CCI [REDACTED] and CCI as determined by ICR per REiNS criteria				
Exploratory	CCI [REDACTED]	Participants who have a CCI [REDACTED] in safety	CCI [REDACTED] CCI [REDACTED] CCI [REDACTED] CCI [REDACTED]	4.2.6
Exploratory	CCI [REDACTED]	Safety	CCI [REDACTED] [REDACTED]	4.2.7
Exploratory	CCI [REDACTED]	Safety	CCI [REDACTED] CCI [REDACTED]	4.2.8
Exploratory	CCI [REDACTED]	Participants who have a CCI [REDACTED] in safety	CCI [REDACTED] [REDACTED]	4.2.9
To evaluate the efficacy of the selumetinib granule formulation by assessment of CCI [REDACTED]				

Statistical category	Endpoint	Population	Population level summary (analysis)	Details in section
Exploratory	CCI [REDACTED]	Safety	Descriptive statistics, estimate LSMeans, and associated 95% CI for MMRM for change from baseline in the CCI [REDACTED]	4.2.10
To evaluate the efficacy of the selumetinib granule formulation by assessment of CCI [REDACTED]				

Exploratory	CCI [REDACTED]	Participants aged < [REDACTED] years at the time of study entry (date of signature of consent) or those who, in the opinion of the Investigator, are unable to [REDACTED] in safety	Descriptive statistics, estimate LSMeans, and associated 95% CI for MMRM for change from baseline in the weekly average	4.2.11
Exploratory	CCI [REDACTED]	Participants aged \geq [REDACTED] years of age at the time of study entry (date of signature of consent) who are able to [REDACTED] in safety	Descriptive statistics, estimate LSMeans, and associated 95% CI for MMRM for change from baseline in the weekly average	4.2.12
Exploratory	CCI [REDACTED]	Safety	Descriptive statistics	4.2.13
Exploratory	CCI [REDACTED]	Safety	Descriptive statistics	4.2.14
Exploratory	CCI [REDACTED]	Safety	Descriptive statistics	4.2.15
To evaluate the safety of the selumetinib granule formulation by assessment of CCI [REDACTED]				

Statistical category	Endpoint	Population	Population level summary (analysis)	Details in section
Exploratory	CCI [REDACTED]	Participants aged < [REDACTED] years in safety at the time of assessment in safety	Descriptive statistics	4.6.13
Exploratory	CCI [REDACTED]	Participants aged \geq [REDACTED] years at the time of assessment in safety	Descriptive statistics	4.6.14

Exploratory	CCI [REDACTED]	Participants aged \geq CCI years at the time of assessment in safety	Descriptive statistics	4.6.15
Exploratory	Physical examination including CCI [REDACTED] CCI	Safety	Descriptive statistics	4.6.12
To evaluate the Pharmacodynamic effect of selumetinib in PBMCs				
Exploratory	Change from baseline in Pharmacodynamic markers, which may include, but may not be limited to, pERK inhibition	Participants weighing \geq 27 kg for pERK in safety	Descriptive statistics	4.3
To determine the PK of selumetinib and N-desmethyl selumetinib after administration of the selumetinib capsule formulation				
Exploratory	Single and multiple dose plasma concentrations and PK parameters of selumetinib and N-desmethyl selumetinib (see Section 4.4 for list of parameters)	PK	Descriptive statistics	4.4
CCI [REDACTED] analyses will be completed to investigate the selumetinib exposure-response relationship for safety, biomarkers and efficacy.				
Statistical category	Endpoint	Population	Population level summary (analysis)	Details in section
Exploratory	CCI [REDACTED] analyses will be completed to assess the effect of CCI [REDACTED] on selumetinib granule and capsule PK, including all paediatric PK data available. In addition, if data allow, CCI [REDACTED] CCI [REDACTED] analyses will be completed to investigate the selumetinib exposure-response relationship for safety, biomarkers and efficacy.	Not defined in the CSR	Details of the CCI [REDACTED] CCI [REDACTED] and CCI [REDACTED] analyses will be described in the modelling analysis plan finalised before database lock. The CCI [REDACTED] and CCI [REDACTED] analyses will be presented separately from the main clinical study report.	NA

AE, adverse event; AUC0-12, partial area under the concentration-time curve from time 0 to 12 hours;

CCI [REDACTED]; CI, confidence

interval; CSR, clinical study report; CTCAE, Common Terminology Criteria for Adverse Events; CCI [REDACTED]

CCI [REDACTED]; CCI [REDACTED]; ECG, electrocardiogram; ECHO, echocardiogram;

CCI [REDACTED]

[REDACTED] CCI [REDACTED] CCI [REDACTED]; LSMEANS, least

square means; MMRM, mixed model repeated measures; MP, metabolite: parent ratio; MRI, magnetic

resonance imaging; NA, not applicable; ORR, objective response rate; PBMC, peripheral blood

mononuclear cell; CCI [REDACTED], CCI [REDACTED] Inventory; pERK, phosphorylated extracellular signal

regulated kinase; CCI [REDACTED]; PK, pharmacokinetics; REiNS, Response Evaluation in

Neurofibromatosis and Schwannomatosis; CCI [REDACTED] CCI [REDACTED] CCI [REDACTED]

4.2.1 Primary Pharmacokinetic Endpoint

The primary PK endpoints are selumetinib AUC0-12 derived after a single dose administration as defined in Section 4.4.

The derivation and analysis of all PK parameters are described in Section 4.4.

4.2.1.1 Primary Analysis of the Primary Endpoint

In the Global Cohorts (Cohorts 1 and 2), the selumetinib AUC0-12 geometric mean and 95% CI (from one sample t-statistic) from single dose administration (Cycle 1 Day 1) will be determined for each age group and total.

4.2.1.2 Supplementary Analyses of the Primary Endpoint

In the Global Cohorts (Cohorts 1 and 2), the selumetinib AUC0-12 geometric mean and CCI [REDACTED] CI (from one sample t-statistic) from single dose administration (Cycle 1 Day 1) will be determined for each age group and total.

Further analyses are described in Section 4.4.

4.2.2 Primary Safety Endpoints

Safety endpoints, derivations, and analysis are described in Section 4.6.

4.2.3 Palatability

4.2.3.1 Definition

An assessment of palatability (the overall appreciation of the product in relation to its smell, taste, aftertaste, and texture) will be conducted using a parent-reported observer palatability assessment. It assesses the willingness to swallow and other observed behaviour on administration of an oral medication.

Assessments will be collected twice daily for Cycle 1 Week 1 and Cycle 7 Week 1. If the assessment cannot be done at Cycle 1 Week 1 and/or Cycle 7 Week 1, then it should be performed as soon as possible afterwards. The Cycle 1 Week 1 and Cycle 7 Week 1 assessments should not be completed if the participants are receiving selumetinib capsules or discontinue study intervention. Additional optional assessments of palatability can be performed for 7 days when a participant changes doses due to a change in BSA.

A copy of the palatability scale is provided in CSP Appendix J 6. The questions are separated in items as follows:

- Item 1: Did your child take their study medication this morning/evening? (Yes/No)
- Item 2: What was the reason for missing the dose? (Only if Item 1 = No)
- Item 3: Choose the response that best matches a description of what you observe of the child's willingness to swallow the study medication (if Item 1 = Yes or [if Item 1 = No and Item 2 = Other])
- Item 4: Was any behaviour observed when the study medication was given to this child that would be indicative of a negative response to the palatability of the study medication? (If Yes, three additional questions will be answered: 1. Did the child turn their head to reject intake of the medication? 2. Did the child twist their face or mouth in an expression of displeasure? 3. Did the child display any other negative behaviour?)
- Item 5: Were you able to prepare and dose the granules according to the Handling Instructions? (If No, one additional question will be answered: If no, please indicate which area/s you had difficulty in following?)

4.2.3.2 Analysis of Palatability

Summaries for cumulative participant disposition and compliance over time (defined in Sections 3.3.9 and 3.3.10, respectively) by each scheduled visit week will be reported.

Derived Number of expected entries, Counts and percentages of completed entries will be summarised for items 1 to 3. Summaries by Cycle 1 Week 1, by Cycle 7 Week 1 and overall will be presented.

For item 2 besides of all responses, the combination of the responses “My child did not want to take the dose / My child could not swallow the medication (indicating palatability issues)” will be presented. For item 3 besides of all responses, the combination of the responses “Swallowed without problem / some resistance but did swallow” and “Spit out some/all medication / vomited up medication” will be presented.

For Items 1 to 3, the percentage distribution of completed entries over the number of expected entries at Cycle 1 Week 1 and Cycle 7 Week 1 will be visualised using a stacked Bar Chart combining all categories responses in the bar of each item, by summing up to 100%. The plot will be repeated separately for Cycle 1 Week 1 and for Cycle 7 Week 1, and overall.

All results will also be listed.

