# 8.2.7.6 Palatability

An assessment of palatability (the overall appreciation of the product in relation to its smell, taste, aftertaste and texture) will be conducted using a parent-reported observer palatability assessment. It is a 3-item measure with dichotomous responses, assessing willingness to swallow and other observed behaviour on administration of an oral medication.

A copy of the palatability scale is provided in Appendix J 6.

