3.3 General Considerations

The below mentioned general principles will be followed throughout the study:

- Descriptive statistics will be used for all variables, as appropriate. Continuous variables will be summarised by the number of observations, mean, standard deviation, minimum, Q1, median, Q3, and maximum. For log-transformed data, it is more appropriate to present geometric mean, geometric coefficient of variation, median, minimum, and maximum. Categorical variables will be summarised by frequency counts and percentages for each category.
- For continuous data, the minimum and maximum will be displayed with the same accuracy as the original data. For laboratory data where decimal precision is provided, the maximum and minimum will be displayed to the standard decimal precision. The mean, median, Q1, and Q3 will be rounded to one additional decimal place compared to the minimum/maximum. The standard

deviation will be rounded to 2 additional decimal places compared to the minimum/maximum.

- For categorical data, percentages will be rounded to one decimal place with the exception of **CCI**, which is presented as a whole number. For 0 results, the percentages will not be included, and only 0 will be presented as a result of the categorical variable.
- Unless otherwise stated, percentages will be calculated out of the population total for the corresponding treatment group.
- Descriptive summaries for all endpoints will be based on the planned visit schedule unless otherwise stated.
- SAS® version 9.4 or above will be used for all analyses.

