3.3.10 Compliance Definition for Clinical Outcome Assessments

Summary measures of compliance over time will be derived for the COAs. These will be based on the following:

- All items/questions completed
- At least meets minimum requirements for calculation of one subscale or a total score of the questionnaire (applicable to **CCI** only)
- At least meets minimum requirement for calculation of the **CCI** (applicable to **CCI**, **CCI** scale only)
- At least one question completed

For COAs with only one question (**CCI**), the category “Questionnaire completed” will be presented.

CCI compliance will be summarised for AM and PM of each visit. The participant will have complied if the **CCI** field of the diary is not missing.

The compliance for palatability will be summarised by item and week and based on the following:

- Expected number of participants
 - A participant is expected to complete Item 2 only if she/he responded ‘No’ at least once to Item 1.
 - A participant is expected to complete Item 3 only if she/he responded “No” at least once to Item 1 and or “Other” to Item 2, or having first responded “Yes” to Item 1.
- Expected number of entries
 - The expected number of diary entries for Items 1, 4, and 5 is; expected number of participants x 2 (number of daily assessments) x the number of days the participant is on treatment without transitioning to capsules in the first week of the Cycle 1 or Cycle 7 (until a maximum of 7 days).
 - The expected number of diary entries for Item 2 is: number of entries (Item 1 = “No”).

- The expected number of diary entries for Item 3 is: number of entries (Item 1 = “No” and Item 2 = “Other”) plus number of entries (Item 1 = “Yes”).
- Subjects with at least one item completed at least once (count and percentage)
 - Percentage will be calculated as the number of participants with item entry completed at least once divided by the expected number of participants in a week.
- Item completion rate (count and percentage)
 - Completion rate will be calculated as the number of actual completed item diary entries divided by the expected number of item diary entries in a cycle.

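### Palatability Item 4 (observed negative behaviour) gets a completion rate and a listing but no specified table of answers, and its expected-entry count ignores the form's skips

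*SAP*

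**What the plan says.** The endpoint table in SAP 4.2 lists palatability as secondary, with descriptive statistics on the safety set: "Palatability will be assessed using the parent-reported observer palatability assessment". SAP 4.2.3.1 gives its content: "It assesses the willingness to swallow and other observed behaviour on administration of an oral medication". Protocol 8.2.7.6 names the same two components: "It is a 3-item measure with dichotomous responses, assessing willingness to swallow and other observed behaviour on administration of an oral medication".

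SAP 4.2.3.2 then sets out the outputs: "Derived Number of expected entries, Counts and percentages of completed entries will be summarised for items 1 to 3". It goes on to full and grouped responses for Items 2 and 3, and a stacked bar chart for Items 1 to 3. It ends: "All results will also be listed". It also calls for the compliance summaries of SAP 3.3.10, where "The compliance for palatability will be summarised by item and week and based on the following". These give, for each item, the participants with at least one completion and the completion rate.

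For the denominator of that rate, SAP 3.3.10 states: "The expected number of diary entries for Items 1, 4, and 5 is; expected number of participants x 2 (number of daily assessments", multiplied by the days on granules in the first week of Cycle 1 or Cycle 7, with a maximum of 7. Items 2 and 3 are treated differently: their expected counts depend on the answers to earlier items.

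On the form (Protocol Appendix J 6), a missed dose leads to a reason. Reasons 2(a), told to skip, and 2(b), forgotten, end the questionnaire. Reasons 2(c), did not want the dose, and 2(d), could not swallow, go straight to Question 4. Reason 2(e), other, goes to Question 3. Protocol 6.1.1 (note to Table 7) and 8.6.1.1 (note b to Table 15) provide for one dose only on Cycle 1 Day 1.

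**The concern.** Item 4 records the second named component of the endpoint: a yes/no question on negative behaviour and, if yes, three yes/no questions on head turning, facial displeasure and any other negative behaviour. Item 3 captures resistance, spitting out and vomiting, but none of these three. After 2(c) or 2(d) the form bypasses Item 3, so for those doses Item 4 is the only description of how the child behaved. If the tables follow SAP 4.2.3.2 as written, a reader learns how often Item 4 was completed but not what was answered, except by counting through the listing.

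The second issue is the completion rate. If entries are expected where the form does not ask the question, correct skips look like missing data.

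**Working it through.** **Which outputs are specified for which item**

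| Item | Answers tabulated or charted (4.2.3.2) | Completion summary (3.3.10) | Listing | Expected count follows the form's routing |
|---|---|---|---|---|
| 2 | Yes | Yes | Yes | Yes |
| 3 | Yes | Yes | Yes | Yes |
| 4 | Not specified | Yes | Yes | No |

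**SAP expected count for Item 4, one child, full week:** 2 × 7 = 14.

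**Cycle 7 Week 1, with k doses ending at 2(a) or 2(b).** The form can yield 14 − k Item 4 entries, so the rate for a correctly completed form is (14 − k)/14:
- k = 1: 13/14 = 92.9%
- k = 2: 12/14 = 85.7%
- k = 3: 11/14 = 78.6%

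The documents give no skip rate, so these values of k are assumptions.

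**Same forms, Item 3 beside Item 4.** Take k = 1 and all other doses given. Item 3 expected = entries with Item 1 = Yes (13) + entries with Item 1 = No and Item 2 = other (0) = 13, so its rate is 13/13 = 100%. Item 4, missed for the same reason on the same form, shows 13/14 = 92.9%.

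**Cycle 1 Week 1.** Planned doses are 1 + 6 × 2 = 13, against 14 expected Item 4 entries. With all 13 doses given, the result depends on the Day 1 evening slot:
- no diary entry: 13/14 = 92.9%
- entry made and answered 2(a) or 2(b): 13/14 = 92.9%
- entry made and answered 2(e): the form continues through Question 3 to Question 4, giving 14/14 = 100%

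**Check of a routed count.** Let expected Item 4 entries = entries with Item 1 = Yes + entries with Item 1 = No and Item 2 = c, d or e. Cycle 7 Week 1 then gives (14 − k)/(14 − k) = 100%. The three Cycle 1 cases give 13/13, 13/13 and 14/14. Removing the Day 1 evening slot as well would give 14/13 = 107.7% in the third case, so no separate exclusion should be added.

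**The case against.** The strongest reply is that the standing rules already cover Item 4. SAP 3.3 says: "Descriptive statistics will be used for all variables, as appropriate", with counts and percentages for categorical variables. The SAP 4.2 table gives descriptive statistics for palatability, and Protocol 9.4.1 provides for all data to be listed and summarised as appropriate. Where the SAP wants a listing only, it says so, as for urinalysis (4.6.4.2), trough concentrations (4.4.2.1) and physical examination (4.6.12.2). It says nothing of that kind about Item 4. This stands in part: an Item 4 table is permitted, and the plan does not withhold the data. But the general lines do not specify one, and the section written for this endpoint limits both its tables and its chart to Items 1 to 3.

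A reader might infer that Item 4 is summarised nowhere outside the listing. The documents do not support that, since SAP 3.3.10 reports its completion by week. A reader might also infer that 14 is certainly wrong for Cycle 1 Week 1. That is not established either: the documents do not say whether a Day 1 evening entry is made, and an answer of 2(e) would still reach Item 4.

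The practical effect is modest. Reasons 2(a) and 2(b) appear in the Item 2 table, so an attentive reader could reconcile a low Item 4 rate. SAP 3.3.10 attaches no threshold to that rate.

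**Conclusion.** The point holds in two parts. First, no summary of Item 4 answers is specified, although observed behaviour is one of the two named components of this secondary endpoint. Second, the Item 4 expected count ignores the stops after 2(a) and 2(b), while Items 2 and 3 are conditioned on earlier answers. Each such dose costs 1/14, about 7.1 percentage points, of one child's weekly completion rate when the form is filled in correctly. The number of such doses is assumed. The single Day 1 dose adds the same loss in Cycle 1 Week 1 only if the evening slot is left blank or ends at 2(a) or 2(b).

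The effect is confined to descriptive outputs; no hypothesis test or decision rule depends on it. It should be corrected because the present wording gives a misleading rate and leaves a named component without a specified table. Two further matters are clarifications, not errors: whether a Day 1 evening entry is made, which settles the Item 1 count at 13 or 14, and whether 2(a) and 2(b) also end the separately numbered handling block (Item 5).

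**What to change.** 1. In SAP 4.2.3.2, add a frequency table of Item 4 (yes/no and the three behaviours) by Cycle 1 Week 1, Cycle 7 Week 1 and overall.
2. In SAP 3.3.10, define expected Item 4 entries as the number of entries with Item 1 = Yes plus the number with Item 1 = No and Item 2 = c, d or e. This equals the existing Item 3 count plus the 2(c) and 2(d) entries. Diary slots with no entry at all remain visible in the Item 1 rate.
3. State whether a Cycle 1 Day 1 evening entry is made, and whether 2(a) and 2(b) end Item 5, and align the Item 1 and Item 5 counts with the answers.

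The cost is a few lines of SAP wording and one added table from diary data already collected.
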